6.2. Data Handling Convention for Efficacy Variables

Rules for handling missing data for primary and secondary efficacy variables are described in Section 5.7.1 and Section 5.7.1.3.

6.3. Data Handling Convention for Missing Data

Missing data will not be imputed in listings. This section includes the methods for missing data imputation for some summary analyses, if necessary.

Date and Time of First/Last Study Treatment

Since the study drug is administered at the site, the date and time of study drug administration are filled in e-CRF. No missing data is expected. Date of first/last administration is the first/last start date of study drug provided in e-CRF.

Adverse Event

If the intensity of a TEAE is missing, it will be classified as “severe” in the frequency tables by intensity of TEAEs. If the assessment of relationship of a TEAE to the investigational product is missing, it will be classified as related to the investigational product.

When the partial AE date/time information does not indicate that the AE started prior to study treatment or after the TEAE period, the AE will be classified as treatment-emergent.

Medication/Procedure

No imputation of medication/procedure start/end dates or times will be performed. If a medication date or time is missing or partially missing and it cannot be determined whether it was taken prior or concomitantly or stopped prior to the first study treatment administration, it will be considered as concomitant medication/procedure.

Potentially Clinically Significant Value (PCSV)

If a patient has a missing baseline value, this patient will be grouped in the category “normal/missing at baseline.”

For PCSVs with 2 conditions, one based on a change from baseline value and the other on a threshold value or a normal range, with the first condition being missing, the PCSV will be based only on the second condition.

For a PCSV defined on a threshold and/or a normal range, this PCSV will be derived using this threshold if the normal range is missing; e.g., for eosinophils the PCSV is >0.5 giga/L or $>ULN$ if $ULN \geq 0.5$ giga/L. When ULN is missing, the value 0.5 should be used.

Measurements flagged as invalid by the laboratory will not be summarized or taken into account in the computation of PCSVs.

6.4. Visit Windows

Visit windows will be programmatically imposed on those efficacy and safety measures repeatedly collected over the course of the study. These visit windows are derived from the number of days in study, specifically assigning day ranges to represent the study assessment schedule provided in the protocol. Data analyzed by time point (including efficacy, laboratory safety data, vital signs, and ECG) will be summarized using the analysis windows given in [Appendix 10.2](#) (i.e. efficacy analysis windows for Part B efficacy and global analysis windows for others). These analysis windows will be applicable for all analyses, and they are defined to provide more homogeneous data for time point-specific analyses. If multiple valid values of a variable exist within an analysis window, the nearest from the targeted study day will be selected for analysis, unless otherwise specified. If the difference is a tie, the value after the targeted study day will be used. If multiple valid values of a variable exist within a same day, then the first value of the day will be selected when time is available, else the scheduled visit will be selected.

6.5. Unscheduled Assessments

For efficacy, safety laboratory data, vital signs, and ECG, unscheduled visit measurements may be used to provide a measurement for a time point, including baseline, if appropriate according to their definitions. The measurements may also be used to determine abnormal values, AESIs, and PCSVs.

6.6. Pooling of Centers for Statistical Analyses

Not applicable.

6.7. Statistical Technical Issues

Not applicable.

7. TIMING OF STATISTICAL ANALYSES

7.1. First Step: PK and Safety Analysis for Part A

The first step will be an analysis of PK data and safety data from all patients in Part A to determine the dose for Part B. The analysis will be performed when at least 8 weeks of concentrations of total evinacumab in serum have been collected and analyzed for all patients in Part A. Subsequent analyses may be conducted using additional accrued PK, LDL-C or safety data if needed to confirm the dose selection for Part B and Part C.

7.2. Second Step: Efficacy and Safety Analysis for Part B

The second analysis will be conducted as soon as all Part B patient data through week 24 have been collected and validated; this will consist of the final analysis of the primary and secondary efficacy endpoints up to week 24 for Part B patients. The safety analysis will be performed on all safety data collected and validated at the time of the second analysis for Part B patients.

The results of the second analysis will not be used to change the conduct of the ongoing study in any aspect. This second analysis may be used for the submission dossier to health authorities.

7.3. Third Step: Final Safety Analysis

The third analysis will be conducted at the end of the study when all Part B and Part C patients have concluded the study, and will consist of the final efficacy and safety analyses.

7.4. Additional Rules

Analyses methods and conventions described in the other sections of this SAP will be applied for all analyses as applicable. The following additional rules will apply for analyses performed at first and second step analyses:

- Any lipid assessments within efficacy analysis windows up to the week 24 visit for Part B will be taken into account (may include few unscheduled lipid data soon after the cut-off date).

- Patients without end of treatment visit performed at the time of the cut-off date will be considered as ongoing and exposed up to the cut-off date.
- Patients who did not complete the respective treatment period nor prematurely discontinued the study treatment at cut-off date will be:
 - Analyzed as “ongoing” in the disposition summary.
 - Their TEAE period and treatment period will end at the respective data cut-off date.
 - Their treatment duration will be derived by considering date of cut-off as last administration date.
 - Analyses of number of IP administrations, and mean IP administration frequency will be performed up to the last administration reported in the e-CRF up to the cut-off date.
 - AEs occurring, worsening or becoming serious after the cut-off date will not be included in the analyses. However, any available outcome before database lock, regardless of timing in relation to the cut-off date, of an adverse event starting prior to the cut-off date will be taken into account. Medications, treatment discontinuations/completions and deaths occurring after the cut-off date will not be included in the analyses.
 - Post-treatment period, and post-study period are not applicable for ongoing patients. Analyses of post-study deaths and post-treatment medications will be performed for patients who either completed or prematurely discontinued the treatment before or at the data cut-off date.
 - Analysis of status at last study contact and proportion of patients with insufficient follow-up will be provided for patients who either completed or prematurely discontinued the treatment before or at the data cut-off date.

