- The total number of patients who completed Part B treatment period as collected on the End of Treatment e-CRF.

- The total number of patients who completed Part B treatment period, defined as at least 20 weeks of study treatment administration and visit week 24 performed.
- The total number of patients who prematurely discontinued Part B treatment, and the reasons for discontinuation collected on the End of Treatment e-CRF
- The total number of patients in Part B who do not proceed into Part C and complete the last study follow-up visit (i.e. Follow-up Week 20).
- The total number of patients in Part B who do not proceed into Part C and do not complete the study follow-up period, defined as the last visit performed less than 22 weeks after the last study treatment administration. Patients who died during the study are excluded.

Patient milestone categories for Part C are defined below. As applicable, percentages will be calculated using a denominator of the number of patients receiving Part C study treatment.

- The total number of patients receiving Part C study treatment.
- The total number of patients ongoing in Part C (applicable for the first step and second step analyses)
- The total number of patients who completed Part C treatment period as collected on the End of Treatment e-CRF.
- The total number of patients who completed Part C treatment period, defined as at least 44 weeks of Part C study treatment administration and Part C visit week 48 performed.
- The total number of patients who prematurely discontinued study treatment during Part C, and the reasons for discontinuation collected on the End of Treatment e-CRF.
- The total number of patients in Part C who complete the last study follow-up visit (i.e. Follow-up week 24).
- The total number of patients who did not complete the study follow-up period, defined as the last visit performed less than 22 weeks after the last study treatment administration. Patients who died during the study are excluded.

The following patient populations for analyses are defined in Section 4.2:

- Efficacy populations (for Part B only): ITT and mITT populations
- Safety analysis set
- Part C safety analysis set
- Pooled safety analysis set
- Anti-evincumab antibody (ADA) analysis set
- Neutralizing anti-evincumab antibody (NAb) analysis set
- Pharmacokinetic (PK) analysis set
- Target analysis set

- Concentration-Response (C-R) analysis set

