5.5. Patient Disposition

Patient disposition includes the description of patient status at major milestone decisions in the study, as well as the patient analysis populations.

Patient study status for the main study part (Part A or Part B) will be summarized by total patients for the study (screened patients, screen failures, and non-enrolled but treated patients only). Summaries will provide the frequency (and percentage as applicable) of patients that met the criteria for the variables described in Section 4.5. Exception listings will be generated for any patient treated but not enrolled, and enrolled but not treated.

Patient analysis populations will be summarized by total patients within main study part (Part A or Part B), depicting frequencies (and percentages) of patients that met the criteria for each population described in Section 3.

For Part C treatment period, the patient study status and patient analysis populations will be summarized for all patients and by main study part (Part A or Part B) in which patients are originally enrolled at the beginning of the study on the Part C safety population for the variables described in Section 4.5.

The incidence of premature study treatment discontinuation (irrespective of the reason) and premature treatment discontinuation due to AEs will be presented graphically by total patients within Part B, or Part C in the respective safety analysis set using the Kaplan-Meier method.

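### SAP 7.4 gives two conflicting tests for 'ongoing' at the step 1 and step 2 cut-offs and does not say which governs a child who stopped drug without an end-of-treatment visit

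*SAP*

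**What the plan says.** SAP 7.4 introduces its list with "The following additional rules will apply for analyses performed at first and second step analyses", so step 3 is outside it. Two consecutive bullets in that list bear on this point.

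- **Visit test.** "Patients without end of treatment visit performed at the time of the cut-off date will be considered as ongoing"; the same sentence also counts them as exposed to that date. No exception is made for a child whose stop has been recorded.
- **Status test.** The next bullet opens "Patients who did not complete the respective treatment period nor prematurely discontinued the study treatment at cut-off date will be" and then lists how such patients are handled. They are shown as ongoing in disposition, and their TEAE and treatment periods end at the cut-off. For exposure, "Their treatment duration will be derived by considering date of cut-off as last administration date". Infusion counts use actual administrations only.

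Elsewhere the SAP works from recorded status. SAP 4.5 reports "The total number of patients who prematurely discontinued Part B treatment, and the reasons for discontinuation collected on the End of Treatment e-CRF". SAP 5.5 plans a Kaplan-Meier display of "The incidence of premature study treatment discontinuation (irrespective of the reason") in Part B and Part C. SAP 4.6 computes Part B exposure from the last Part B infusion plus 28 days, and SAP 6.3 expects no missing infusion dates.

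**The concern.** The two tests agree for most children. They part for a child who stops evinacumab and leaves without an EOT visit: ongoing by the visit test, discontinued by the status test and by the e-CRF source in SAP 4.5. Such a child is possible. Protocol 8.4.2 asks a withdrawing patient to complete the final assessments, but attendance cannot be assured. Protocol 8.4.2 and 9.1.2 also call the visit after stopping drug an unscheduled or early-termination visit with EOT assessments. The SAP does not say whether that visit counts as the EOT visit in 7.4.

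Children who leave abruptly are the most informative drop-outs for tolerability. If the visit test were applied to one of them, the exposure table would credit treatment that was never given and a stop could be missing from disposition. The 7.4 analysis of insufficient follow-up, limited to patients who completed or discontinued, could omit the child too. The errors in exposure and disposition would both run in the favourable direction, in a step 2 analysis that SAP 7.2 says may support a submission.

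**Working it through.** The plan states no figure on this point, so the check applies its own exposure formula to one child under each rule.

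**Inputs**
- Exposure in weeks (SAP 4.6): (last infusion day + 28 − first infusion day) / 7.
- Last scheduled Part B infusion: week 20, day 141 (Protocol 8.1 and Table 2).
- Part B size: 14 (Protocol 11.2, Amendment 2). The SAP, written for Amendment 1, has 18.
- TEAE period: to last infusion + 168 days (SAP 4.8.1).
- Assumed: infusions on days 1 and 29 only, no EOT visit, all other children at full exposure. The documents give no cut-off date, so a range of study days is shown.

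**Formula check.** A completer has (141 + 28 − 1)/7 = 24.0 weeks, which matches the 24-week treatment period.

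**Child who stopped, by actual last infusion.** (29 + 28 − 1)/7 = 8.0 weeks. Mean over 14: (13 × 24 + 8)/14 = 22.9 weeks.

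**Same child treated as ongoing, cut-off on study day c.** There are two readings. Exposed to the cut-off gives (c − 1)/7. Taking the cut-off as the last administration date and adding the 28 days of SAP 4.6 gives (c + 28 − 1)/7.

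| Assumed c | Exposed to cut-off (weeks) | Cut-off as last infusion, + 28 days (weeks) | Mean over 14, by reading (weeks) |
|---|---|---|---|
| 169 | 24.0 | 28.0 | 24.0 / 24.3 |
| 253 | 36.0 | 40.0 | 24.9 / 25.1 |
| 365 | 52.0 | 56.0 | 26.0 / 26.3 |
| 533 | 76.0 | 80.0 | 27.7 / 28.0 |

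For c = 365 the means are (312 + 52)/14 = 26.0 and (312 + 56)/14 = 26.3. If the cut-off falls when the last child reaches day 169, c = 365 means that this child was enrolled 365 − 169 = 196 days (28 weeks) before the last one. With 18 children the mean moves from (17 × 24 + 8)/18 = 23.1 to (408 + 52)/18 = 25.6 or (408 + 56)/18 = 25.8 weeks.

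**Other outputs**
- One stop lost from disposition would be 1/14 = 7.1% (1/18 = 5.6%).
- The TEAE period should end on day 29 + 168 = 197. Run to a cut-off on day 365, it is 168 days too long. With a cut-off on day 169 there is no excess.
- Infusion counts would stay at two, beside about a year of credited exposure.
- The primary LDL-C analysis defines its on-treatment period by the last administration + 35 days (SAP 5.7.1). SAP 7.4 substitutes the cut-off as last administration only for treatment duration, so the estimate does not move.

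**The case against.** The best defence is that SAP 7.4 read whole does not prescribe the misclassification. The detailed handling rules all sit under the status test, which excludes children who prematurely discontinued. Later sub-bullets again set apart those who completed or discontinued by the cut-off. The section also keeps the SAP's other conventions where applicable, including the e-CRF source for discontinuations. On this view the visit test is only a lead-in to the bullet after it.

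The affected group is also small. Step 2 is run after all Part B data through week 24 are in, so a child still ongoing in Part B would itself be an anomaly, and the rule mainly serves children in Part C. The protocol asks for a visit with EOT assessments as soon as possible after drug is stopped.

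Much of this stands, and it rules out a stronger reading. A reader might infer that such a child is bound to be recorded as still on treatment, that Part B would report 0/14 discontinuations in place of 1/14, and that the child would be censored in the Kaplan-Meier display. The documents do not support that. SAP 4.5 has an ongoing line only for Part C. Its Part B list counts stops from the e-CRF and asks for a patient listing with reasons. SAP 5.5 states no censoring rule for the discontinuation plot.

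The defence does not remove the conflict. The visit test carries its own consequence, exposure to the cut-off, without exception, and nothing says that the status test overrides it. Two programmers could follow the text and produce different tables.

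**Conclusion.** SAP 7.4 contains two conflicting tests for ongoing status, with no order of precedence. Misclassification of a child who stopped and left without an EOT visit is possible, not certain. If it happened once in 14 children with a cut-off on study day 365, that child's exposure would read 52.0 or 56.0 weeks in place of 8.0. Mean Part B exposure would read 26.0 or 26.3 weeks in place of 22.9, above the 24.0 weeks that the schedule yields. A discontinuation worth 7.1 percentage points could be lost from the summaries.

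These sizes rest on assumed cut-off days and on one hypothetical child; the documents give no expected frequency. The effect is confined to steps 1 and 2 and to exposure, disposition, the discontinuation display, and the TEAE and treatment periods. The point should be settled because the sample is small, the true last infusion date is known, and the error would flatter the drug.

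**What to change.** Delete the visit-based bullet and let the status test govern. Alternatively, restrict it along these lines: *Patients with no EOT visit and no recorded completion, permanent discontinuation, study withdrawal, death or loss to follow-up by the cut-off date are considered ongoing.* For all other patients, derive exposure, treatment period and TEAE period from the actual last infusion date by the standard SAP definitions, and take disposition from the End of Treatment e-CRF, whether or not an EOT visit took place.

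The cost is one sentence in the SAP and one changed flag in programming. Children who are truly ongoing are handled as before. The only downside is that the exposure and disposition tables may look slightly less favourable.

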4.6. Study Treatment Exposure and Compliance Variables

Study treatment exposure variables for infusions administered in Part A are listed below with associated definitions:

- The total number of Part A study treatment infusions by patient.
- Patient duration of Part A observation treatment period in weeks defined as: (last visit date during the Part A observation period - first study treatment administration date in Part A)/7.

Study treatment exposure variables for infusions administered in Part B are listed below with associated definitions:

- Patient duration of Part B study treatment exposure in weeks defined as: (last Part B study treatment administration date +28 – first Part B study treatment administration date)/7. Unplanned intermittent discontinuations in study treatment will be addressed on a case-by-case basis, since this is expected to be a rare occurrence. Values will be rounded to one decimal place.
- The total number of Part B study treatment infusions by patient.
- The following categories will be used for treatment exposure at 4 week intervals: ≥ 1 day and < 4 weeks, ≥ 4 weeks and < 8 weeks, ≥ 8 weeks and < 12 weeks, ≥ 12 weeks and < 16 weeks, ≥ 16 weeks and < 20 weeks, ≥ 20 weeks and < 24 weeks, ≥ 24 weeks.

Study treatment exposure variables for infusions administered in Part C are listed below with associated definitions:

- Patient duration of Part C study treatment exposure in weeks defined as: (last Part C study treatment administration date +28 – first Part C study treatment administration date)/7. Unplanned intermittent discontinuations in study treatment will be addressed on a case-by-case basis, since this is expected to be a rare occurrence. Values will be rounded to one decimal place.
- The total number of Part C study treatment infusions by patient.
- The following categories will be used for treatment exposure at 4 week intervals: ≥ 1 day and < 4 weeks, ≥ 4 weeks and < 8 weeks, ≥ 8 weeks and < 12 weeks, ≥ 12 weeks and < 16 weeks, ≥ 16 weeks and < 20 weeks, ≥ 20 weeks and < 24 weeks, ≥ 24 weeks and < 28 weeks, ≥ 28 weeks and < 32 weeks, ≥ 32 weeks and < 36 weeks, ≥ 36 weeks and < 40 weeks, ≥ 40 weeks and < 44 weeks, ≥ 44 weeks and < 48 weeks, ≥ 48 weeks

Study treatment exposure variables on the integrated data pool (Section 2.4) are listed below with associated definitions:

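### For patients still on treatment at the step 1 or step 2 cut-off, the SAP's exposure rule runs 28 days past the cut-off, contradicting its own statement that exposure stops there

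*SAP*

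**What the plan says.** SAP Section 4.6 defines exposure in weeks for Part B as "last Part B study treatment administration date +28 – first Part B study treatment administration date)/7" and for Part C as "last Part C study treatment administration date +28 – first Part C study treatment administration date)/7". Pooled exposure is the sum of the relevant parts, so it inherits whatever the Part B and Part C formulas give. Part A is handled differently: its duration is "last visit date during the Part A observation period - first study treatment administration date in Part A)/7", with no 28 days added.

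SAP Section 7.4 gives extra rules for the first- and second-step analyses. It opens with a general statement: "Analyses methods and conventions described in the other sections of this SAP will be applied for all analyses as applicable". Patients who have had no end-of-treatment visit by the cut-off "will be considered as ongoing and exposed up to the cut-off date". For patients who have neither completed nor stopped treatment, two sub-rules follow: "Their TEAE period and treatment period will end at the respective data cut-off date", and "Their treatment duration will be derived by considering date of cut-off as last administration date". Infusion counts and infusion frequency use only infusions actually recorded up to the cut-off.

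SAP Section 4.5 expects patients to be ongoing in Part C at both of these steps. SAP Section 7.2 allows the second-step analysis to be used in a regulatory submission.

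**The concern.** The 28 days in Section 4.6 stand for the dosing interval that follows a real infusion. Section 7.4 puts the cut-off in the place of the infusion date and does not switch the 28 days off. A programmer who follows both sections literally credits an ongoing patient with four weeks that have not yet happened. A programmer who follows the statement that exposure stops at the cut-off does not. The same data could therefore give two exposure tables 4 weeks apart.

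At stake is the description of how long these children have been treated, in tables that may support a submission. The extra 28 days would also not match the neighbouring outputs, because no infusion or adverse event after the cut-off is counted.

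**Working it through.** **Inputs.** F = first dose day (day 1 of the part). L = actual last dose day. C = cut-off day. Formula from SAP Section 4.6: (last + 28 − first)/7. Doses are every 28 days, on Part C days 1, 29, 57 and so on (SAP Appendix 10.2, Table 4). Exposure categories are 4 weeks wide, with an open top category of 48 weeks or more in Part C.

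**Check of the formula on a completer.** The last Part B dose is at week 20, day 141: (141 + 28 − 1)/7 = 24.0 weeks. This is the planned Part B treatment period, so the formula works when the last dose is a real one.

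**Ongoing patients, three versions.**

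- As written: replace L by C, giving (C + 28 − F)/7.
- Stopped at the cut-off: (C − F)/7.
- Ordinary convention with the actual last dose: (L + 28 − F)/7.

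As written minus stopped at the cut-off = 28/7 = 4.0 weeks, whatever C is. As written minus the ordinary convention = (C − L)/7, the time since the last infusion.

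| Part C cut-off day | On-schedule last dose day | Stopped at cut-off (weeks) | As written (weeks) | Actual last dose + 28 (weeks) | As written minus actual + 28 (weeks) |
|---|---|---|---|---|---|
| 15 | 1 | 2.0 | 6.0 | 4.0 | 2.0 |
| 99 | 85 | 14.0 | 18.0 | 16.0 | 2.0 |
| 200 | 197 | 28.4 | 32.4 | 32.0 | 0.4 |
| 309 | 309 | 44.0 | 48.0 | 48.0 | 0.0 |
| 330 | 309 | 47.0 | 51.0 | 48.0 | 3.0 |

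For day 200: (200 + 28 − 1)/7 = 32.4; (200 − 1)/7 = 28.4; (197 + 28 − 1)/7 = 32.0. Relative to stopping at the cut-off, 4.0/28.4 = 14%.

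**Categories.** Against stopping at the cut-off, a 4-week excess moves a patient up exactly one 4-week category, unless the patient is already in the open top one. Against the actual last dose plus 28 there is no move when dosing is on schedule. With the last dose on day 1 + 28j, the ordinary result is 4(j + 1) weeks, and the as-written result lies from 4(j + 1) to below 4(j + 2), which is the same category.

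**Total.** The documents do not say how many patients will be ongoing. Planned enrolment in Protocol Section 11.2 is 6 + 14 = 20. If all were ongoing, 20 × 4 = 80 patient-weeks against stopping at the cut-off.

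**Protocol formula.** Protocol Section 11.4.5.3 adds 1 day to the same expression. That day appears in every version and leaves the 28-day gap unchanged.

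**The case against.** The best defence is that the intent can be recovered. Section 7.4 ends both exposure and the treatment period at the cut-off, other conventions apply only where applicable, and a cut-off is not an infusion, so the 28 days should not be added. This is a tenable guess at what was meant. It does not repair the text: the sentence on treatment duration names the input to the formula, and nothing removes the 28 days.

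The defence is stronger on size. Several larger claims are tempting, and the documents do not support them.

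- A reader might infer that every ongoing patient gains a full 4 weeks and a category over the SAP's usual convention. That convention already credits the interval after the last infusion, so with on-schedule dosing the gain is under 4 weeks and the category does not change.
- A reader might take 80 patient-weeks as the expected overstatement. It assumes that every planned patient is ongoing. Part A patients enter Part C well before the last Part B patient reaches week 24, and some may have finished by then.
- A reader might infer that safety rates or the final results are distorted. Adverse-event tables are counts and percentages of the safety set, infusion-reaction rates divide by infusions received, and adverse-event periods end at the cut-off. The primary endpoint does not use exposure, and the third-step analysis is run once patients have finished the study.

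A simple switch to (C − F)/7 is also imperfect. It gives 0 for a patient first dosed on the cut-off day, although the lowest exposure category starts at 1 day, and it credits gaps left by missed doses.

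**Conclusion.** The inconsistency is real: taken literally, the SAP ends an ongoing patient's exposure 28 days after the cut-off, while the same section says it ends at the cut-off. The excess is 4.0 weeks per patient against stopping at the cut-off. Against the actual last dose plus 28 it is 0 to under 4 weeks, assuming infusions exactly every 28 days; a late or skipped infusion makes it larger, since it equals the time since the last dose.

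The effect is confined to the step 1 and step 2 exposure-duration summaries for Part B, Part C and the pool. In practice it bears mainly on patients ongoing in Part C, because step 2 waits for all Part B data through week 24. Part A duration, infusion counts, adverse-event periods, efficacy and the final analysis are unaffected. It should be corrected because the interim tables may be submitted, but it does not threaten the trial's conclusions.

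**What to change.** In SAP Section 7.4, replace the sentence on treatment duration with a single stated rule. For example: for ongoing patients, exposure ends at the earlier of the actual last administration date plus 28 days and the cut-off date, the cut-off day is counted, and no further 28 days are added. As a formula: (min(L + 28, C + 1) − F)/7.

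For Part C day 200 this gives (min(225, 201) − 1)/7 = 28.6 weeks, against 32.4 as written. A patient first dosed on the cut-off day gets 1 day and falls in the lowest category. A patient who has missed infusions is not credited beyond 28 days after the last one. For completers the Section 4.6 formula stays as it is.

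The cost is one line of SAP text and one line of programming. The only downside is that interim exposure figures come out slightly smaller.
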